All attempts will be made to collect all data per protocol. No imputations will be conducted for missing values. Outliers identified during the PK analysis will be discussed in the analysis report.

Missing data analysis methods

Imputation rules for missing or partial adverse event start/stop dates

- If the AE start date day is missing (month and year provided) then set the date to the first of the
 month unless the month and year are the same as the first dose of study drug. In this case, set the
 date to the date of first dose.
- If the AE start date month is missing (year is provided) then set the month and day to January 1, unless the year is the same as the year of the first dose. In this case, set the date to the date of first dose.
- If the AE end date day is missing (month and year provided) then set the date to the last day of the month.
- If the AE end date month is missing (year is provided) then set the date to December 31.

• If the year of the AE start date or AE end date are missing, then a query to the site must be made to gather additional information. If the end date and start date are both missing, then no imputation will be done. If the stat date remains missing but the end date is before first dose date, then the AE will be considered before treatment. If the end date is after the first dose, then the AE will be considered to have been treatment emergent.

Imputation rules for missing or partial medication start/stop dates

Start Date:

- If only day is missing, use the first day of the month.
- If day and month are missing, use the first day of the year.
- If day, month, and year are missing use the first day of the year with the same year as the first dose.

End Date:

- If only day is missing, use the last day of the month.
- If day and month are missing, use the last day of the year.
- If day, month, and year are missing assign 'continuing' status to the stop date.

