8.4.4 Prior and concomitant medications

Medications used in this study will be coded by using MedDRA version 23.0.

Prior medications are defined as those medications with a start date 28 days prior to the initial screening.

Concomitant medications are defined as those medications with a start state later than 28 days prior to the initial screening and will be recorded at screening visit. At each subsequent study visit each new concomitant medication and changes to existing medications will be recorded. Subjects will be required not to utilize non-study medication or herbal supplements during the study except those deemed necessary by the site Principal Investigator (PI) or sub investigator. Any drug (e.g., over-the-counter herbal supplement, vitamins or prescription) used by the subject during the course of the trial will be recorded in the subject's source documents and on the appropriate eCRF. Per protocol section 5.2 exclusion criteria #20, subjects using any of the prohibited medications within 28 days prior to screening or planned use during the study period will be excluded from the study. However, if any prohibited medication is used during study period by any enrolled subject, it would be captured as a protocol deviation at local sites.

Prior and concomitant medications will be summarized descriptively using frequency tables by Anatomical Therapeutic Chemical (ATC) class and preferred name by treatment group on the ITT population and presented separately for the following groups:

- · Medications prior to 28 days before the initial screening.
- Concomitant medications continued after initial screening.
- Concomitant medications started at or after the initial screening.
- Prior and concomitant use of any restricted medications as described in protocol exclusion criteria.

Details for imputing missing or partial start and/or stop dates of medication are described in section 7.3.

Extent of exposure

A single dose of study product will be administered on-site by research personnel at Day 1 (Visit 2 per protocol v7.0) for all subjects. All study products will be administered via IM injection. Thus, treatment compliance will not be applicable.

Efficacy analysis

Efficacy analysis is only applicable to the secondary endpoints regarding immunogenicity described in section 4.2 and analysis methods are described in section 8.6.5 below.

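### The medication start-date rules lack the dosing-date check and site query that the AE rules have, so some drugs started after dosing are tabulated as pre-study use

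*SAP*

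**What the plan says.** SAP Section 6.0, under missing data analysis methods, sets out two lists of date rules.

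For adverse events, a start date with only the day missing becomes the first of the "month unless the month and year are the same as the first dose of study drug". With the month missing it becomes 1 January, "unless the year is the same as the year of the first dose". For both exceptions the instruction is: "In this case, set the date to the date of first dose". For a missing year: "If the year of the AE start date or AE end date are missing, then a query to the site must be made to" obtain more information. If the start date stays missing, the end date decides whether the event counts as treatment emergent.

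For medication start dates there are three unconditional rules: "If only day is missing, use the first day of the month"; "If day and month are missing, use the first day of the year"; and, for a fully missing date, "If day, month, and year are missing use the first day of the year with the same year as the first dose". None of them looks at the dosing date, the stop date or the visit at which the drug was reported. A fully missing stop date is read as ongoing use.

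SAP Section 8.4.4 applies these rules and tabulates medications in groups set by start date: before the 28 days preceding screening (prior), continued after screening, and "Concomitant medications started at or after the initial screening". It also has each new drug recorded at the visit where it is reported.

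**The concern.** The plan protects adverse events from being moved to before the injection by an incomplete date, but gives medications no such protection and states no reason for the difference. Because Section 8.4.4 sorts drugs by start date, an imputed date can move a drug from one table to another. A drug taken for the first time after dosing can then appear as something the subject was already using before the study.

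At stake is the description of medication use in a first-in-human safety study. The displacement is always backwards, so drug use begun on study can only be understated. In the listings, an adverse event and the drug taken for it could carry the same partial date, with the event placed on the dosing date and the drug before it.

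**Working it through.** The plan states no figure on this point, so the rules were applied to calendar dates.

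**Inputs.** Screening runs from Day -14 to Day -2 (SAP Section 3.0; Protocol Section 8.1). The study-day formula in SAP Table 3 has no Day 0, so screening is s = 2 to 14 days before dosing. Assumption, not in the documents: the dosing date is equally likely to be any day d = 1 to 365 of the year.

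**Fully missing date.** The imputed start is day 1 of the dosing year.

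| Imputed start is | Condition | s = 2 | s = 14 |
|---|---|---|---|
| before dosing | d > 1 | 364/365 = 99.7% | 364/365 = 99.7% |
| before screening | d > s + 1 | 362/365 = 99.2% | 350/365 = 95.9% |
| more than 28 days before screening (prior) | d > s + 29 | 334/365 = 91.5% | 322/365 = 88.2% |

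**Day and month missing.** If the stated year is the dosing year, the imputed date is again 1 January of that year and the table applies unchanged. Weighting each dosing date by the days left in its year, because early dosing leaves more room for a later start, gives 99.5% before dosing, 92% to 98% before screening and 78% to 84% in the prior group. If the stated year is later than the dosing year, 1 January of that year is after dosing.

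**Day missing.** Only a start in the dosing month is affected. With dosing on day m of the month, the first of the month is m - s - 1 days before screening, at most 31 - 2 - 1 = 28. It is never more than 28 days before, so the drug does not reach the prior group. At most it moves from started at or after screening to continued after screening. Among post-dose starts in the dosing month, 93% are dated before dosing and 25% to 81% before screening.

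**How far the partial-date rules reach.** Further assumption: true starts spread evenly from Day 2 to Day 365 (Cohort 5) or Day 540 (Cohorts 1-4). The share of post-dose starts moved to before dosing is then 3.8% or 2.6% with the day missing, and 49.7% or 33.6% with day and month missing.

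**Example, dosing on 15 June 2021.**
- True start 20 June 2021, day missing: becomes 1 June 2021, before dosing.
- True start 20 July 2021, day missing: becomes 1 July 2021, still after dosing.
- True start 10 September 2021, day and month missing: becomes 1 January 2021, prior group.
- True start 10 February 2022, day and month missing: becomes 1 January 2022, still after dosing.

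**Size in a table.** One misfiled user is 1/8 = 12.5 percentage points of a cohort's active arm, or 1/40 = 2.5 points if the active arms are pooled.

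**The case against.** A reader might infer that any incomplete date on a post-dose drug is pulled to before dosing. The rules do not do that. The known part has to match the dosing month or year, and most day-missing dates stay after dosing.

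Nor does a date before dosing by itself change a table, since the Section 8.4.4 groups turn on screening and on 28 days before it. In the first month, where day-missing dates could be affected, medications are reviewed on Days 2, 3, 4, 8, 15 and 30, so an unknown day is less likely. The long gaps come later, up to 185 days between Day 180 and Day 365, and bear mainly on missing months and fully missing dates.

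A reader might also infer that a planned analysis linking drugs to adverse events is damaged. Neither document plans one, and the adverse event fields in Protocol Section 9.3.1 do not list treatment given. The mismatch would show only in listings.

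Finally, Protocol Section 13 sends missing data and anomalies back to the sites, so some medication dates would be completed before any rule is applied.

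All of this stands, and it narrows the point. It does not remove it. For dates still fully missing after queries, or known only to the dosing year, the written rule usually puts a post-dose drug in the prior group, although the visit of first report is collected and would show otherwise.

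**Conclusion.** The point holds for fully missing start dates and for partial dates that match the dosing month or year. A fully missing date, or one known only to the dosing year, is imputed before screening for 96% to 99% of dosing dates and into the prior group for 88% to 92%. These shares assume dosing dates uniform over a year and screening 14 to 2 days before dosing. A missing day in the dosing month at most moves a drug between the two concomitant groups.

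The bias has one direction, towards understating drug use begun on study. Only descriptive medication tables and listings are affected; no test, primary endpoint or sample size statement depends on them. The documents do not give the frequency of incomplete dates, so the number of misfiled records cannot be estimated. This is a minor correction, worth making because it is cheap.

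**What to change.** Amend the medication start-date rules in SAP Section 6.0 as follows:

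- Query the site for a missing year, as for adverse events.
- For a drug first reported after dosing, set the start to the dosing date if the start date is still fully missing, or if its known month and year (or year alone) match dosing. Never impute a start later than a recorded stop date.
- For a drug recorded at screening or on Day 1 before dosing, keep the existing rules, but cap the imputed start at the date of that record.

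With this check, no drug that truly started after dosing is imputed to before dosing under any of the three rules. The cost is a few sentences in the SAP and a small programming change that uses the visit of first report, which is already collected. The downside is small: a few pre-existing drugs that subjects did not report before dosing will count as started on study.

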7.0 Statistical Methods

General statistical conventions

All statistical procedures will be completed using SAS version 9.4 (or higher), R version 4.0.0 (or higher), or Phoenix WinNonLin 8.3.1 (or higher).

Unless otherwise stated, all statistical testing will be two-sided and will be performed using a significance (alpha) of 0.05. Two-sided 95% confidence intervals (CI) will be provided when relevant.

Continuous variables will be summarized using descriptive statistics, including number of subjects (n), mean, median, standard deviation (SD), interquartile ranges (IQR), minimum, and maximum.

For categorical variables, summaries will include counts of subjects and percentages. Percentages will be rounded to one decimal place.

For summary purposes, baseline will be defined as the last available pre-dose value. All summaries will be presented by treatment group, unless otherwise specified.

All subject data, including those derived, will be presented in individual subject data listings. Unless otherwise stated, unscheduled visit results will be included in date/time chronological order, within patient listings only. All listings will be sorted by subject ID, date/time and visit. The treatment group will be stated on each listing. Unless otherwise stated, data listings will be based on FAS.

Unscheduled data points will not be used in any summary tables separated by visit but will be presented in each listing as appropriate.

Subject disposition

Subject disposition information will be summarized by dosing cohort, treatment group and overall. The number and percentage of subjects who are enrolled, who complete the study, and who withdraw early from the study will be presented.

The primary reasons for early withdrawal will also be tabulated, including withdrawal by subject, physician decision, lost to follow-up, major protocol deviation or other.

The number of subjects enrolled will be used as the denominator for the percentage calculation. Subject disposition will be listed.

The number and percent of subjects in each analysis set will also be tabulated. A listing of each subject excluded from an analysis population will be listed as well as the reason why they were excluded from the population.

Treatment Misallocations: if a subject is

- Randomized but withdrawn prior to dosing, then they will be replaced and will not be included in any analysis.
- Randomized but receive incorrect treatment, they will be reported under the treatment they actually
 have received for all safety analysis and PK analysis.

Protocol deviations

The number of patients excluded from FAS/ITT, Safety, and Per-protocol analysis sets and reasons for exclusion will be summarized by treatment group and overall.

Population membership details will be listed, including reason for exclusion from each population.

Protocol deviation data are not captured in the clinical database and therefore will not be reported individually within the scope of the SAP. Protocol deviations will be summarized in the final clinical study report.

Demographics and baseline characteristics

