8.18. Unscheduled Visit

A subject may return to the clinic for an unscheduled visit at any time. The following activities at a minimum should be performed:

- Obtain vital signs (blood pressure, heart rate, respiratory rate, and oral temperature)
- Perform symptom directed PE as appropriate

- Review and update concomitant medications
- Assessment of Aes and SAEs

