- 12. Serum from subjects who give consent for future use samples will be collected at 2 hr and 4 hr post dose and on days 2, 8, and 30
- 13. Vital signs (sitting for at least 10 minutes) will be checked just before injection and every visit.
- 14. The subject will be under direct observation during at least the initial 30 minutes of dosing. A physical examination will be performed at approximately 30 minutes post injection or in response to subject symptoms which will include the following: General appearance including alertness, diaphoresis, chills, and any difficulty breathing, HEENT, Chest, Heart, Skin and Joints
- 15. Draw prior to dosing at baseline
- 16. The Hypersensitivity Panel includes cytokine and complement panels, IgE, and tryptase. Draw 14ml prior to dosing. If a subject develops anaphylaxis or anaphylactoid reaction, an additional 10 mL sample will be drawn during the event, and another will be drawn after the event
- 17. Subjects in all cohorts will receive RT-PCR testing at screening, Day 1 prior to dosing, and at presentation of symptoms.
- 18. SARS-CoV-2 antibodies will only be tested in Cohorts 1-4 (Not applicable for Cohort 5)
- 19. TC visits will be conducted for only Cohorts 1-4 (Not applicable for Cohort 5).

Study Endpoints

Primary endpoint(s)

- The occurrence of Serious Adverse Events following administration of ADM03820 to the final follow-up visit.
- The occurrence of adverse events (AEs) from administration of ADM03820 to the final follow-up visit.
- The occurrence of changes from baseline in physical examination, vital signs, and clinical safety laboratory values following administration of ADM03820 to the final follow-up visit.

Secondary endpoint(s)

Resilience Government Services. ADM03820-001

- The assessment of C_{max}, T_{max} and AUC_(0-t) for total antibodies of ADM03820 as measured by Enzyme-linked Immunosorbent Assay (ELISA) for samples from Cohorts 1 and 2. The assessment of C_{max}, T_{max} and AUC_(0-t) for each of the monoclonal antibodies of ADM03820 as measured by enzyme-linked immunosorbent assay (ELISA) for samples from Cohort 3,Cohort 4 and Cohort 5.
 - o Pharmacokinetic samples will be tested by ELISA at pre-dose, 2, 4, 8, and 24 hours post dose, and on Days 3, 4, 8, 15, 30, 45, 60, 90, 120, 150, 180, and 365 for all cohorts
 - Samples will be tested by Microneutralization at pre-dose and Days 2, 15, 30, 60, 90, 120, 150, and 180 for all cohorts

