8.7.2 Clinical laboratory evaluations

Clinical laboratory evaluations include serum chemistry, hematology, and urinalysis. For the purposes of summarization in both the tables and listings, all laboratory values will be presented in SI units. If a lab value is reported using a nonnumeric qualifier e.g., less than (<) a certain value, or greater than (>) a certain value, the given numeric value will be used in the summary statistics, ignoring the nonnumeric qualifier; but will be listed as is in the listings. Severity of abnormal laboratory results will be graded according to CTCAE v5.0.

All laboratory data obtained between screening visit and the end of study will be used for the laboratory safety analysis. Laboratory summaries will be provided including values measured during the follow-up period, where appropriate.

Visit value and change and from baseline during the treatment period will be summarized by treatment group using descriptive statistics for all laboratory parameters.

Abnormal clinical laboratory results will be summarized by treatment group and severity at subsequent visits following screening when clinical safety labs are performed. Abnormality will be determined according to the pre-specified criteria at each site (which may vary by sites) and flagged in EDC.

Subjects with graded laboratory values will be identified in listings, including patient information, visit date, severity of abnormality, relationship to study product along with specifics of the abnormal laboratory results and corresponding normal ranges (when applicable).

Resilience Government Services, ADM03820-001 Version: Final v4.0, Date: 11-SEP-2023
BST1302-SOP-T01/v1.0/2020 Page 23 of 26

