8.7.3 Vital signs

Visit values and changes from baseline for vital sign measurements (blood pressure, oral temperature, heart rate and respiratory rate) will be summarized by treatment group at each visit or timepoint using descriptive statistics. Visit values will be calculated as the mean of all available measurements per parameter. Subjects with vital signs will be listed and summarized by treatment group.

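### Unscheduled lab and vital-sign values are barred from the by-visit tables, and no other planned summary of the any-time primary safety endpoint says that it includes them

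*SAP*

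**What the plan says.** The third primary endpoint (SAP, Study Endpoints; Protocol 3.2.1) is "The occurrence of changes from baseline in physical examination, vital signs, and clinical safety laboratory values following administration of ADM03820", counted up to the last follow-up visit. It asks whether a change happened at any time, not at a particular visit.

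The general conventions in SAP 7.0 set two rules for unscheduled results. The first is a default that allows exceptions: "Unless otherwise stated, unscheduled visit results will be included in date/time chronological order, within patient listings only". The second has no exception clause: "Unscheduled data points will not be used in any summary tables separated by visit but will be presented in each listing as appropriate".

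The analysis sections then name these displays:

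- **Laboratory, SAP 8.7.2.** "Visit value and change and from baseline during the treatment period will be summarized by treatment group using descriptive statistics for all laboratory parameters", and "Abnormal clinical laboratory results will be summarized by treatment group and severity at subsequent visits following screening when clinical safety labs are performed". The same section says: "All laboratory data obtained between screening visit and the end of study will be used for the laboratory safety analysis".
- **Vital signs, SAP 8.7.3.** Values and changes from baseline "will be summarized by treatment group at each visit or timepoint using descriptive statistics". A further sentence promises a listing and a treatment-group summary of subjects with vital signs. It seems to lack a qualifier such as graded or abnormal.
- **Adverse-event section, SAP 8.7.1.** It plans a descriptive summary of the changes named in the endpoint and a category for laboratory abnormalities. Neither has a visit split.
- **Protocol 11.3.3.2.** It plans laboratory shift tables by toxicity grade. SAP 8.7.2 does not mention them, and the SAP's section on changes from the protocol lists only the added per-protocol population.

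On the source of unscheduled data, Protocol 8.18 says: "A subject may return to the clinic for an unscheduled visit at any time". The minimum set there is vital signs, a symptom-directed examination as appropriate, medication review and adverse-event assessment. Laboratory tests are not in it.

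**The concern.** Unscheduled visits are often made because the subject feels unwell, so their values are more likely than routine ones to be abnormal. A rule that keeps them out of tables by visit is ordinary practice and does no harm when another table collects each subject's worst post-dose value from all sources. Neither 8.7.2 nor 8.7.3 specifies such a table. The remaining summaries are silent on unscheduled values, so the listings-only default decides.

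At stake is the tabulated result for part of a primary endpoint in cohorts of 8 active subjects, where one subject moves the observed rate by 1/8 = 12.5 percentage points. Within a group, the omission can only lower the count of subjects with a change.

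**Working it through.** **1. The displays side by side**

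| Display | Split by visit? | Unscheduled values |
|---|---|---|
| Lab values and change (SAP 8.7.2) | Yes | Barred |
| Abnormal labs by severity (SAP 8.7.2) | Yes, at the visits with safety labs | Barred |
| Vital-sign values and change (SAP 8.7.3) | Yes, by visit or timepoint | Barred |
| Subjects with vital signs (SAP 8.7.3) | Not stated | Silent, so the default applies |
| Occurrence of changes from baseline (SAP 8.7.1) | No | Silent, so the default applies |
| Laboratory abnormalities category (SAP 8.7.1) | No | Silent, so the default applies |
| Lab shift by toxicity grade (Protocol 11.3.3.2) | Not stated | Silent; not carried into SAP 8.7.2 |

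The statement in 8.7.2 that all laboratory data are used could be the exception that the default allows. It does not mention unscheduled results, and it cannot override the second rule for tables by visit. It also has no counterpart for vital signs.

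**2. The plan's own precision figures**

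With 8 active subjects (Protocol 11.1):

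- P(at least one event) = 1 − (1 − p)^8. At p = 0.15 this is 1 − 0.85^8 = 0.7275. At p = 0.5 it is 1 − 0.5^8 = 0.9961.
- The exact 95% upper bound for 0/8 is 1 − 0.025^(1/8) = 0.3694.

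These match the stated 0.728, 0.996 and 0.369.

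**3. Effect of one omitted subject**

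Suppose one active subject in a cohort has an abnormal value only at an unscheduled visit, and it is not reported as an adverse event.

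- Shown: 0/8, exact 95% CI 0 to 36.9%.
- True: 1/8 = 12.5%. The lower limit is 1 − 0.975^(1/8) = 0.0032. The upper limit solves (1 − p)^8 + 8p(1 − p)^7 = 0.025, which gives p = 0.5265. The interval is 0.3% to 52.7%.

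The denominator of 8 follows Protocol 11.3.3, which summarizes by dose cohort and control group. The SAP says treatment group without defining any pooling. At the other extreme, with all 5 × 8 = 40 active subjects pooled, the pair would be 0/40 (upper bound 8.8%) against 1/40 (2.5%, 0.06% to 13.2%).

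**4. Where scheduled data are thin**

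Post-dose safety labs fall on Days 8, 15, 30, 90, 180 and 365 (Protocol 7.5.2), so the gaps are 7, 15, 60, 90 and 185 days. Vital signs are taken at every clinic visit, and their longest gap is also 365 − 180 = 185 days. For Cohorts 1-4 the contacts after Day 365 are telephone calls (Protocol 8.16 and 8.17). In those last 540 − 365 = 175 days, any measured value would have to come from an unscheduled visit.

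**The case against.** The case for leaving the plan alone has real weight. A reader might infer that the SAP plans no laboratory or vital-sign summary across visits, so that such a value would reach no table at all. The documents do not support that. SAP 8.7.1 restates the endpoint as a summary with no visit split and adds a laboratory abnormalities category. SAP 8.7.3 has a second vital-sign summary, and the protocol plans laboratory shift tables that the SAP does not declare withdrawn. The statement in 8.7.2 on using all laboratory data may be meant as the exception.

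There is also a route through adverse events. The protocol's definition of an adverse event includes an abnormal laboratory finding (9.1), new or worsened examination findings are to be reported as adverse events (7.2), and adverse events are assessed at every unscheduled visit (8.18). All values are listed, and listings for 8 active subjects can be read directly. Safety endpoints are not tested, and dose escalation rests on the committee's review of all available safety data (Protocol 9.5.3), not on these tables. The table shells are a separate document (SAP 1.0) that was not available.

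These points narrow the concern without removing it. None of the summaries lacking a visit split says that it takes in unscheduled values, and the default says they do not unless stated. The adverse-event route depends on the event being reported. A listing shows the value but does not place the subject in the numerator of a primary-endpoint table.

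**Conclusion.** The point holds as a conflict and a gap in the specification. Under the default, a value seen only at an unscheduled visit can be left out of the summaries of an any-time primary safety endpoint. Whether it would be left out of all of them is not settled by the text. Vital signs are the clearest case; a laboratory value arises only if a sample is drawn.

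The size is one subject in 8 for each such case: 0/8 (upper bound 36.9%) shown instead of 1/8 (12.5%, 0.3% to 52.7%). This assumes tabulation by dose cohort, no other qualifying change in that subject, no adverse-event report and table shells that follow the SAP text. The documents give no expected number of such cases. The rule applies to active and control subjects alike, so it lowers counts in either group and has no fixed direction for the difference between them.

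A reader might also size the problem from the fact that counts by visit do not add up to subjects ever affected. That is true of scheduled data as well and is a separate limitation, so it does not measure the effect of excluding unscheduled values. The same added table would remedy both.

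**What to change.** In SAP 8.7.2 and 8.7.3, specify a subject-level table of the worst post-dose CTCAE grade for each graded laboratory and vital-sign parameter, or of the shift from baseline grade to that worst grade, by dose cohort and control. State that it uses all post-dose values, including unscheduled and repeat ones, and that this is the exception allowed by the general conventions. Say how a reading repeated for suspected measurement error is treated (Protocol 7.3 allows such repeats).

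In the same edit:

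- Reconcile the statement in 8.7.2 on using all laboratory data with the conventions in 7.0.
- Complete the unfinished vital-sign sentence in 8.7.3.
- Say whether the SAP 8.7.1 summary of changes includes unscheduled values.
- Restore the protocol's laboratory shift tables, or list them as dropped in the section on changes from the protocol.

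Keep the tables by visit on scheduled values. The cost is SAP wording and one or two extra tables from data already collected, with no new procedures for subjects or sites.
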